6.15. End of Study Visit/Early Termination Visit

The End of Study (EOS)/Early Termination (ET) Visit will occur 7 days after last dose (± 2 days) for Part 1 (SAD) and 7 days after the last dose (± 2 days) for the MAD part of the study. This visit can also take place if a subject withdraws early from the study.

A serum pregnancy test will be performed for WOCBP. Hematology and coagulation, biochemistry, and urinalysis will be performed. The subject will be asked about AEs and prior and concomitant medications and an ECG will be conducted. Every attempt will be made for collection of data from withdrawn subjects via attendance to an EOS/ET Visit.

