Appendix 1 Schedule of Assessments - SAD

	Screening	Treatment			Follow Up/ ET/EOS ¹
Study Day	-28 to -2	-1	1	2 ²	7 (±2)
Informed Consent	X				
Inclusion/Exclusion Criteria ³	X	X			
Randomization ⁴		X			
Height and BMI	X				
Medical History and Demographics	X				
Physical and Neurological Exam ⁵	X	X	X	X	X
Vital Signs ⁶	X	X	X	X	X
Laboratory Tests ⁷					
Serology	X				
Hematology	X	X	X	X	X
Serum Chemistry	X	X	X	X	X
Urinalysis ⁸	X	X	X	X	X
Coagulation	X	X	X	X	X
Pregnancy Test ⁹	X				X
Drug of Abuse Screening ¹⁰	X	X			
Alcohol Breath Test	X				
Study Drug Administration ¹¹			X		
PK Assessments ¹²			X	X	
Biomarker Sample ¹³		X	X		X
EEG ¹⁴	X		X	X	
12-Lead ECG ¹⁵	X	X	X	X	X
Adverse events	X	X	X	X	X

	Screening	Treatment			Follow Up/ ET/EOS ¹
Concomitant Medications	X	X ³	X	X	X
Inpatient Component ¹⁶	X	X	X	X	

Abbreviations: BMI = body mass index; ECG = electrocardiogram; EEG = electroencephalography; ET = early termination; EOS = end of study; PK = pharmacokinetics; SAD = single ascending dose.

¹ All subjects will be required to attend an ET/EOS visit, even if they have withdrawn or been removed from the study. For completed subjects, this will be at Day 7.

² For sentinel subjects this will include a follow up phone call at 48 hours.

³ Confirmation of eligibility based on inclusion/exclusion criteria.

⁴ Randomization to occur after confirmation of eligibility on Day -1 and prior to dosing on Day 1.

⁵ An abbreviated neurological examination will be undertaken to include: light touch/power in limbs, brief cranial nerve examination and recording of any other abnormal movements; to occur on Day-1, Day 1 predose and at 30 minutes (\pm 15 minutes) postdose, and Day 2. Physical and neurological examination on Day 2 should be performed pre-discharge.

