Appendix 2 Schedule of Assessments – MAD

	Screening	Treatment									ET/EOS ¹
Study Day	-28 to -2	-1	1	2	3	4	5	6	7	8 ²	14 (± 2)
Informed Consent	X										
Inclusion/Exclusion criteria ³	X	X									
Randomization ⁴		X									
Height and BMI	X										
Physical and Neurological Exam ⁵	X	X	X	X	X	X	X	X	X	X	X
Gastrointestinal Symptoms ⁶	X	X	X	X	X	X	X	X	X	X	X
Vital Signs ⁷	X	X	X	X	X	X	X	X	X	X	X
Concomitant Medications	X	X	X	X	X	X	X	X	X	X	X
Laboratory Tests ⁸											
Serology	X										
Hematology	X	X	X	X		X		X	X	X	X
Serum Chemistry	X	X	X	X		X		X	X	X	X
Urinalysis	X	X	X	X		X		X	X	X	X
Coagulation	X	X	X	X		X		X	X	X	X
Pregnancy Test ⁹	X	X									X
Drug Abuse Screening	X	X ¹⁰									
Alcohol Breath Test	X	X ¹⁰									
Study Drug Administration ¹¹			X	X	X	X	X	X	X		
PK Assessments ¹²			X			X ¹²			X		
Biomarker Sample ¹³		X	X	X	X				X		X

Study Day	Screening	Treatment									ET/EOS ¹
	-28 to -2	-1	1	2	3	4	5	6	7	8 ²	14 (± 2)
12-Lead ECG ¹⁴	X	X	X	X	X	X	X	X	X		X
EEG ¹⁵	X		X	X	X	X	X	X	X	X	
C-SSRS ¹⁶	X					X			X		
Adverse Events	X	X	X	X	X	X	X	X	X	X	X
Inpatient component ¹⁷	X	X	X	X	X	X	X	X	X	X	

Abbreviations: BMI = body mass index; C-SSRS = Columbia Suicide Severity Rating Scale; ECG = electrocardiogram; EEG = electroencephalography; EOS = end of study; ET = end of treatment; PK = pharmacokinetics; MAD = multiple ascending dose; SAD = single ascending dose.

¹ All subjects required to attend an ET/EOS visit, even if they have withdrawn or been removed from the study.

² Day 8 is 24-hours (± 1 hour) after administration of the last morning dose. This visit will be used to collect the “24-hour” assessments.

³ Confirmation of eligibility based on inclusion/exclusion criteria.

⁴ Randomization to occur after confirmation of eligibility on Day -1 and prior to the first dose on Day 1.

⁵ An abbreviated neurological examination will be undertaken to include: light touch/power in limbs, brief cranial nerve examination up to 1 hour prior to the first dose and at 30 minutes (± 15 minutes) post morning dose.

⁶ An assessment of bowel movements including any incidence of constipation or changes in bowel habits will be conducted daily. On Day -1 and Day 1, the gastrointestinal screening assessments will be conducted as part of physical examinations. On Days 2, 3, 4, 5, 6, 7, 8 and Day 14, a gastrointestinal questionnaire will be administered within 30 minutes prior to morning dosing.

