5 GENERAL CONSIDERATIONS

5.1 General Data Handling

All safety analyses will be conducted based on SAS 9.4 or higher.

Placebo subjects will be pooled across cohorts.

Data in the clinical database as well as vendor data will be presented in by-subject data listings.

Continuous data will be summarized by study part and cohort based on n, mean, median, standard deviation (SD), first quartile (Q1), third quartile (Q3), minimum value, and maximum value.

Categorical data will be summarized by study part and cohort using frequency counts and percentages. Unless otherwise stated, the denominator of percentages will be the number of participants in the population/cohort or the number with non-missing data.

- In summaries pertaining to subject demographics and subject disposition, the number of missing values will be presented as a separate category with no percentage, but only if one or more subjects are missing data.
- Counts of zero will be presented without percentages.

No inferential statistics will be produced for any safety endpoints.

Relative to the number of digits after the decimal in the raw data, summary statistics will have the following number of digits after the decimal:

- Minimum and Maximum: same number of significant digits as the raw data
- Mean, Median, Q1, and Q3: one additional significant digit
- SD: two additional significant digits
- Percentages <100% will be reported to one decimal place and percentages of 100% will be reported with no decimal place. The number and percentage will be presented in the form of XX (XX.X%). Percentage values of less than 0.1% will be presented as XX (<0.1%).
- Summary statistics will not exceed four digits after the decimal. Some laboratory parameters or other data may require deviation from this rule.

For clinical laboratory data, results reported as below the lower limit of quantification (LLOQ) or above the upper limit of quantification (ULOQ) will be replaced by the LLOQ and ULOQ, respectively, to ensure inclusion in applicable tables and figures, but will be presented in applicable listings as originally reported.

All data up to the time of study completion/withdrawal from the study will be included in the analysis, regardless of duration of treatment.

Numbering for data displays will be based on International Council for Harmonization (ICH) E3.

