5.2 General Definitions

Variable	Definition
Study Day	
 • Study Day = date of interest – treatment start date + 1, when the date of interest \geq treatment start date; • otherwise, Study Day = date of interest – treatment start date. 
Note: if either date is missing, Study Day calculations will not be performed. Should imputation be performed, then Study Day may be computed, where appropriate.

Baseline	
For ECG data, baseline is defined as the average of up to three measurements taken at the pre-dose timepoint on the Day 1 Visit if available; otherwise, baseline is defined as the last single tracing measurement taken prior to the first dose of study treatment.
 
For EEG data, baseline is defined as the assessment collected at the Screening Visit (Day -2) in which the patient was in a sleep deprived state.
 
For all other endpoints, baseline is defined as the last non-missing value collected prior to receiving the first dose of study treatment (based on date and time of administration as applicable). For endpoints with both planned pre-dose and post-dose timepoint assessments on Day 1, only pre-dose assessments will be considered as a candidate for baseline. For MAD Cohort 3, vital signs

	assessments on Day 1 associated with the second dose (i.e., evening) will not be considered as a candidate for baseline.
Post-baseline	Defined as values collected after receipt of the first dose of study treatment (based on date and time of administration as applicable)
Change from Baseline	Defined as: Post-baseline value – Baseline value
Duration on Study (in days)	End of study date – randomization date + 1
BMI (kg/m ²)	BMI is collected in the clinical database
Age (yr)	Age is collected in the clinical database
Study Completion	Defined as attendance at the End of Study (EOS) Visit.

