6 ANALYSIS METHODS

6.1 Study Subject Data

6.1.1 Subject Disposition

The number and percentage of subjects in each analysis population and final subject status (completed or withdrawn), including study discontinuation reasons, will be produced based on the number of randomized subjects. Data will be presented by study part and cohort.

Subjects contributing to each analysis population and final disposition status will be listed. Failed eligibility criteria for screen failures will also be included in a data listing. Alcohol breath test and drug screening results will be included in a data listing.

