6.1.6 Study Drug Exposure and Compliance

Study drug administration information recorded on the CRF will be presented in a data listing for the SAF population.

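### A subject withdrawn from the study who attends the shared ET/EOS visit is both completed and withdrawn under the SAP, and no SAP table shows who stopped dosing

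*SAP*

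**What the plan says.** SAP 5.2 (General Definitions) defines study completion in one phrase: "Defined as attendance at the End of Study (EOS) Visit". It sets no condition on doses received, on withdrawal status or on whether the visit was the scheduled one.

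SAP 6.1.1 (Subject Disposition) uses that status in a two-way split: "final subject status (completed or withdrawn), including study discontinuation reasons, will be produced based on the number of randomized subjects".

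The protocol does not separate an early termination visit from an end of study visit. Section 6.15 describes one EOS/ET visit and says: "This visit can also take place if a subject withdraws early from the study". Appendices 1 and 2 give it one column each. Footnote 1 of Appendix 1 (SAD) reads: "All subjects will be required to attend an ET/EOS visit, even if they have withdrawn or been removed from the study". Footnote 1 of Appendix 2 (MAD) says the same: "All subjects required to attend an ET/EOS visit, even if they have withdrawn or been removed from the study".

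Two further SAP statements bear on the point. Section 5.1 sets the data rule: "All data up to the time of study completion/withdrawal from the study will be included in the analysis, regardless of duration of treatment". Section 6.1.6 deals with exposure: "Study drug administration information recorded on the CRF will be presented in a data listing for the SAF population".

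**The concern.** The primary objective is safety and tolerability. How many subjects left the study or could not finish dosing, and why, is a basic tolerability result, above all in Part B, where dosing runs for 7 days. If the completion rule in SAP 5.2 is applied as written, a subject withdrawn for an adverse event or for an ECG or EEG finding, who then attends the required visit, can be counted as completed.

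The other planned outputs do little to make up for this. AEs leading to discontinuation are part of the primary endpoint in Protocol 8.5.1 and SAP 2, but neither the TEAE overview nor the SOC/PT tables in SAP 6.4.1 include them. Dosing is listed, not summarised. The disposition table is therefore the only summary in the SAP that shows discontinuation and its reasons, and it rests on the ambiguous definition.

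A second, weaker worry concerns data. If a subject is classed as withdrawn, a programmer could take SAP 5.1 to stop at the withdrawal date and leave out the laboratory tests, ECG and AEs that the protocol seeks from that subject afterwards.

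**Working it through.** The plan states no completion or withdrawal rate, so there is no figure to reproduce. The check sets the texts side by side and adds one piece of illustrative arithmetic.

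**1. Does attendance identify completers?** SAP 5.2 makes attendance sufficient. Protocol 6.15 and both appendices make attendance mandatory for completers and for withdrawn or removed subjects alike. Attendance therefore cannot separate the two groups. The protocol itself treats completers as a subset of attendees; Appendix 1 footnote 1 adds: "For completed subjects, this will be at Day 7".

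**2. Is there a tie-break?** SAP 5.2 names EOS, not ET, but the SAP defines no separate ET visit. SAP 5.4 summarises by the nominal visit on the CRF, which does not help if ET and EOS are one visit. SAP 3.5 speaks of completing EOS and of discontinuing as alternatives, which hints at the intent. Protocol 6.21.1 requires a primary reason for withdrawal in the eCRF. Neither text says that a recorded withdrawal overrides attendance.

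**3. Which subjects are affected?** Protocol 6.21.2 separates stopping treatment from leaving follow-up, and 6.21.3 keeps treatment discontinuers in safety follow-up to EOS.

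| Subject | Study status under SAP 5.2 | Correct? | Early stop of dosing shown in an SAP table? |
|---|---|---|---|
| Finishes dosing, attends scheduled EOS | Completed | Yes | Not applicable |
| Stops drug only, followed to EOS | Completed | Yes | No |
| Withdrawn from study, attends ET/EOS | Completed and withdrawn | Ambiguous | Only if classed as withdrawn, and then as a study discontinuation |
| Withdrawn from study, does not attend | Withdrawn | Yes | As a study discontinuation |

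**4. The data rule.** Protocol 6.15 seeks data from withdrawn subjects at a visit that follows withdrawal. SAP 5.1 covers data up to withdrawal and does not define when withdrawal occurs. If the date is the day the subject is withdrawn, the ET data lie outside the rule as worded. If it is the date of the ET visit, nothing is lost. SAP 6.4.1 counts as treatment-emergent any AE with onset or worsening after the first dose, with no closing date, and that conflicts with the first reading.

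**5. Illustrative size.** Inputs: 6 KNX100 subjects per cohort (Protocol 3.1); w subjects withdrawn from the study who attend ET/EOS (assumed); r of them replaced (Protocol 6.21.1 replaces withdrawn subjects who are not evaluable). The denominator is randomized subjects (SAP 6.1.1).

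- Completion with attendance as the rule: (6 + r)/(6 + r) = 100%.
- Completion with withdrawn subjects excluded: (6 − w + r)/(6 + r).

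| w | r | Attendance rule | Withdrawn excluded |
|---|---|---|---|
| 0 | 0 | 6/6 = 100% | 6/6 = 100% |
| 1 | 0 | 6/6 = 100% | 5/6 = 83.3% |
| 1 | 1 | 7/7 = 100% | 6/7 = 85.7% |
| 2 | 0 | 6/6 = 100% | 4/6 = 66.7% |
| 2 | 2 | 8/8 = 100% | 6/8 = 75.0% |

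**The case against.** The best defence is that the intent can be worked out. SAP 3.5 treats EOS completion and discontinuation as alternatives, the eCRF holds a withdrawal reason, and SAP 6.1.1 tabulates study discontinuation reasons. A subject with a recorded reason would be expected in that part of the table, and showing full completion would require the programmer to ignore the record. This lowers the likelihood of the error. It does not correct the stated rule, which a prespecified plan should not leave to inference.

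The defence is stronger on three inferences a reader might draw.

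- **That every early stopper is miscounted.** The documents do not support this. A subject who stops drug and stays in follow-up to EOS is correctly a study completer under Protocol 6.21.2 and 6.21.3. What is missing for that subject is a treatment status.
- **That safety data after withdrawal will be lost.** SAP 5.1 is an inclusion statement and nowhere excludes later data. SAP 5.4 summarises by nominal visit, the Safety Set in SAP 4.1 has no withdrawal cutoff, SAP 6.4.1 lists all AEs, and SAP 5.1 itself provides by-subject listings. Loss is a possible reading, not a demonstrated result.
- **That a known share of each arm is misreported.** No withdrawal rate is stated, so any percentage is hypothetical.

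It also stands that dose escalation does not depend on the completion label: the CRC reviews discontinuations due to AEs directly (Protocol 9.8.1, SAP 3.4). Part A is single-dose, so an early stop of dosing cannot arise in 4 of the 7 planned cohorts, although withdrawal before EOS can. With 8 subjects per cohort, the listings would show each case to a careful reader.

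**Conclusion.** The point holds in a limited form. On its wording, SAP 5.2 makes a completer of a subject withdrawn from the study who attends the required ET/EOS visit, while SAP 6.1.1 also has a withdrawn category for the same subject, and nothing in the SAP settles which applies. Separately, no table listed in the SAP shows subjects who stopped dosing but completed follow-up. The data rule in SAP 5.1 is unclear for withdrawn subjects and sits badly with the open-ended TEAE definition in SAP 6.4.1.

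The actual size is unknown. It is nil if nobody withdraws. One affected subject shifts a KNX100 arm's completion by 16.7 percentage points (100% − 83.3%), or 14.3 (100% − 85.7%) with replacement. This assumes that the subject attends and that attendance alone is used to set status. The study is descriptive, so no hypothesis test, error rate or power is affected. Severity is minor to moderate: worth settling before database lock because it touches a tolerability result, but not a threat to the trial's conclusions.

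**What to change.** - **SAP 5.2:** define study completion as attending the scheduled EOS visit with no study withdrawal recorded. Define treatment completion separately as receiving all planned doses. Making treatment completion a condition of study completion would be a mistake, since it would label fully followed treatment discontinuers as study non-completers. The planned dose count must first be reconciled for Part B Cohort 3: the protocol Synopsis gives 14 doses, whereas Protocol 3.1 gives 7 for every Part B subject.
- **SAP 6.1.1:** tabulate treatment status (completed or discontinued, with reason) separately from study status (completed or withdrawn, with reason).
- **SAP 5.1:** state that all data collected through the ET/EOS visit and AE follow-up enter the safety summaries, whatever the withdrawal date.

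The cost is a few sentences and one extra block in the disposition table. Dosing information and the primary reason for discontinuation or withdrawal are already recorded (SAP 6.1.6, Protocol 6.21.1). The reported completion rate may come out lower.

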5.3 Data Imputation Rules

Generally, missing data will not be imputed, and will be presented as collected in the study database.

In cases where adverse event or medication dates are missing, the imputation methods described in Appendix 1 will be used to determine flags for treatment-emergent events and concomitant medications.

Other missing data methods will be described within the respective analysis section, as appropriate.

5.4 Visit Windows

Data will be summarized using the recorded nominal visit values in the CRF; no visit date windowing will be conducted. Unscheduled visit data may be included in summaries of baseline, minimum/maximum post-baseline, and incidence of subjects with potentially clinically significant post-baseline results. Unscheduled visits will also be presented in applicable data listings.

In general, if multiple non-missing values are available at the same visit/timepoint then the later value will be used in the analysis. In cases where multiple non-missing values are on the same date and time, the value with the larger Study Data Tabulation Model (SDTM) record sequence number will be used in the analysis.

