6.5. Vital Signs

Vital signs will be recorded at screening, study entry, and at all visits before and after dosing of study drug, including:

- body temperature,
- respiratory parameters (including respiratory rate, saturated oxygen, pulse oximetry),
- pulse rate,
- heart rate (after 3-minute semi-supine rest), and
- arterial blood pressure (systolic and diastolic; after 3-minute rest in either a semi-supine or sitting position).
- peak flow measurement.

During the inpatient dosing period, vital signs also include respiratory rate, continuous pulse oximetry and saturated oxygen, which will be undertaken via telemetry within 2 hours predose and at 2 hours postdose (\pm 15 minutes) as per the schedule in [Appendix 1](#) and [Appendix 2](#). For MAD Cohort 3, vital signs, including telemetry will be conducted following each dose (am and pm).

Peak flow measurement will also be undertaken within 1 hour predose as well as at 1-, 2-, and 4-hours (\pm 15 minutes) postdose. For MAD Cohort 3, peak flow measurements will be conducted following each dose (am and pm). The highest of 3 peak flow measurements, at each timepoint shall be recorded.

Protocol Exclusions 2 and 3 pertaining to vital signs should be checked at both Screening and Day -1 to confirm eligibility. Following the Day-1 eligibility check, any subject with vital signs outside of acceptable range will have their vital signs repeated. If the readings are again abnormal, but not clinically significant, it is at the PI's discretion as to whether to continue the subject in the study. Normal vital sign ranges for this study are presented in [Appendix 4](#).

For details regarding timing for assessments, please refer to the SOA in [Appendix 1](#) and [Appendix 2](#).

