6.17.9. Clinical Laboratory and Investigational Findings Adverse Events

Abnormal laboratory findings and other abnormal investigational findings (for example, on an ECG trace) should not be reported as AEs unless they are associated with clinical signs and symptoms, lead to treatment discontinuation, or are considered otherwise medically important by the investigator. If a laboratory abnormality fulfills these criteria, the identified medical condition (i.e., anemia, increased alanine aminotransferase [ALT]) must be reported as the AE rather than the abnormal value itself.

The investigator must review the laboratory report, document this review, and record any clinically relevant changes occurring during the study in the AE section of the CRF. The laboratory reports must be filed with the source documents. Clinically significant abnormal laboratory findings are those which are not associated with an underlying disease, unless judged by the investigator to be more severe than expected for the subject's condition.

All laboratory tests with values considered clinically significantly abnormal during participation in the study or within 1 day after the last dose of study drug should be repeated until the values return to normal (or baseline) or are no longer considered clinically significant by the investigator or medical monitor. If such values do not return to normal/baseline within a period of time judged reasonable by the investigator, the etiology should be identified, and the Sponsor notified.

All protocol-required laboratory assessments must be conducted in accordance with the laboratory manual and the SOA in [Appendix 1](#) and [Appendix 2](#). If laboratory values from non-protocol specified laboratory assessments performed at the institution's local laboratory require a change in subject management or are considered clinically significant by the investigator (e.g., SAE, AE, or dose modification), then the results must be recorded in the CRF.

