6.4.3 Vital Signs

Vital signs and body measurements include: height (cm); weight (kg); BMI (kg/m²); systolic and diastolic blood pressure (mmHg); heart rate (beats/min); respiratory rate (breaths/min); oxygen saturation (%); temperature (°C); and the highest of 3 peak flow measurements (L/min) taken on Day 1 will be recorded on the CRF. Observed values and changes from baseline for vital signs will be summarized by study part and cohort at each visit and time point.

Potentially clinically significant post-baseline results will be summarized by study part and cohort at each visit and timepoint.

Vital Sign	Criteria
Systolic BP	> 150 mmHg > 200 mmHg ≤ 80 mmHg
Diastolic BP	> 100 mmHg > 110 mmHg
Heart Rate	< 50 bpm > 120 bpm ≥ 30 bpm increase from baseline ≥ 30 bpm decrease from baseline
Respiratory Rate	< 8 breaths/min > 24 breaths/min
Oxygen Saturation	< 95%
Temperature	> 38.3°C increase of ≥ 1.1°C from baseline

All vital signs results will be provided in by-subject data listings.

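### SAP 5.4 keeps the later of two readings at a timepoint, but vital signs are re-measured only when out of range, so potentially clinically significant counts can be biased downward

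*SAP*

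**What the plan says.** - SAP 5.4 (Visit Windows), qualified as holding in general: "if multiple non-missing values are available at the same visit/timepoint then the later value will be used in the analysis". If date and time are also identical, the record with the larger sequence number is taken.
- SAP 5.4 on unscheduled data: "Unscheduled visit data may be included in summaries of baseline, minimum/maximum post-baseline, and incidence of subjects with potentially clinically significant post-baseline results". The verb is *may*, and the sentence concerns unscheduled visits.
- Protocol 6.5 (Vital Signs), after the Day -1 eligibility check: "any subject with vital signs outside of acceptable range will have their vital signs repeated". The ranges are in Appendix 4.
- SAP 6.4.3 (Vital Signs): "Potentially clinically significant post-baseline results will be summarized by study part and cohort at each visit and timepoint". Observed values and changes are also tabulated by visit and timepoint. No minimum/maximum summary is planned for vital signs.
- Protocol 6.17.9: laboratory values considered clinically significantly abnormal "should be repeated until the values return to normal (or baseline) or are no longer considered clinically significant by the investigator or medical monitor".
- SAP 6.4.2: thyroid PCS results are summarised by visit, and chemistry and hematology shifts by visit/timepoint. Minimum and maximum post-baseline laboratory values are also summarised.
- Two kinds of planned repeat have their own rules: ECG triplicates are averaged (SAP 6.4.5), and the highest of three peak flows is recorded (Protocol 6.5).

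**The concern.** A later-value rule is harmless when repeats are taken regardless of the result. Here the unplanned vital-sign repeats depend on the first reading being abnormal. An abnormal first reading can be replaced by a normal re-test, while a normal first reading is left as it is. Selection works in one direction only.

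Vital signs and laboratory tests are among the primary safety endpoints (Protocol 8.5.1), and each cohort has six subjects on KNX100, so one lost PCS case visibly changes a table. The SAP does not say whether a re-test is filed under the nominal timepoint or as unscheduled, or whether a superseded first reading still counts towards PCS incidence or the minimum/maximum.

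**Working it through.** The plan states no figure on this point, so there is nothing to reproduce. The check has two parts.

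**1. Does every PCS reading trigger a repeat?** Absolute limits from SAP 6.4.3 against the ranges in Protocol Appendix 4:

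| Sign | Normal range | PCS limits | Always out of range? |
|---|---|---|---|
| Systolic BP (mmHg) | 90–140 | >150, >200, ≤80 | yes |
| Diastolic BP (mmHg) | 40–90 | >100, >110 | yes |
| Heart/pulse rate (bpm) | 50–100 | <50, >120 | yes |
| Respiratory rate (per min) | 10–22 | <8, >24 | yes |
| Oxygen saturation (%) | ≥95 | <95 | yes |
| Temperature (°C) | 35.5–37.5 | >38.3 | yes |

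All 11 absolute limits lie at or outside the range. For two of them (heart rate <50, saturation <95%) the trigger equals the limit; for the other nine the trigger is wider. The change-from-baseline criteria (heart rate change of at least 30 bpm, temperature rise of at least 1.1°C) can be met within range and need not trigger a repeat.

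**2. How much could be lost?** Let X1 be the first reading and X2 the re-test, standardised, exchangeable and bivariate normal with correlation ρ. Let a be the trigger and b the PCS limit, in SDs from the mean, with a ≤ b.

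- First-reading rate: P(X1 > b)
- Later-value rate: P(X1 > a and X2 > b)
- Any-reading rate: P(X1 > b) + P(X1 > a and X2 > b) − P(X1 > b and X2 > b)

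Direction: P(X1 > a and X2 > b) ≤ P(X2 > b) = P(X1 > b). Under exchangeability the later-value rate can never exceed the first-reading rate.

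*Trigger equals limit (a = b):*

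| Limit | ρ | First reading | Later value | Ratio |
|---|---|---|---|---|
| 1.5 SD | 0.7 | 6.7% | 2.8% | 42% |
| 1.5 SD | 0.9 | 6.7% | 4.4% | 66% |
| 2 SD | 0.7 | 2.3% | 0.7% | 32% |
| 2 SD | 0.9 | 2.3% | 1.3% | 59% |

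With an assumed 5% first-reading rate, the later-value rate is 2.0% (ρ 0.7) or 3.2% (ρ 0.9). The chance of tabulating at least one case among six active subjects at one timepoint falls from 1 − 0.95⁶ = 26.5% to 11.2% or 17.7%.

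*Trigger wider than limit: systolic BP >150, trigger >140, with a = (140 − mean)/SD and b = (150 − mean)/SD:*

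| Assumed mean/SD | a, b | ρ | First | Later | Later/first | Any | Any/first |
|---|---|---|---|---|---|---|---|
| 120/12 | 1.67, 2.50 | 0.7 | 0.62% | 0.41% | 66% | 0.88% | 142% |
| 120/12 | 1.67, 2.50 | 0.9 | 0.62% | 0.60% | 96% | 0.90% | 144% |
| 125/15 | 1.00, 1.67 | 0.7 | 4.78% | 3.46% | 72% | 6.39% | 134% |
| 125/15 | 1.00, 1.67 | 0.9 | 4.78% | 4.56% | 95% | 6.31% | 132% |

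The loss is smaller here because a first reading between 140 and 150 is also repeated, and some of those repeats exceed 150.

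**The case against.** The strongest reply has four parts.

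- **The rule is hedged and depends on labelling.** It applies in general, and only to values at the same visit/timepoint. If re-tests are entered as unscheduled, the first reading stays in its timepoint summary. This stands: replacement is conditional. But the documents do not say how re-tests are labelled, and *may* commits the analyst to nothing.
- **Confirmation is part of the protocol's logic.** Protocol 6.19 considers whether a result remains out of range after repetition, and the vital-sign withdrawal limits in 6.21.1 refer to repeat analysis. The later value is therefore a recognisable convention. That supports reporting confirmed values as well; it does not justify removing the first reading from an incidence table without saying so.
- **Other channels keep the information.** Listings hold all vital-sign results, and dose escalation rests on committee review of the safety data (Protocol 9.8.1), not on these tables. This limits the consequences. Adverse event capture is a weaker backstop: under Protocol 6.17.9 an abnormal finding is not an adverse event unless it is accompanied by signs and symptoms, leads to discontinuation or is judged medically important.
- **An any-reading rule has its own bias.** This stands: in the systolic example it gives 132 to 144% of the first-reading rate.

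A reader might also infer stronger things that the documents do not support. Not all repeats follow abnormality: ECGs and peak flow are repeated by design under other rules. Overall safety incidence is not affected: treatment-emergent adverse event counts do not use this rule, and no vital-sign shift table is planned. Nor is there a basis for saying that laboratory abnormalities would tend to vanish. Only values judged clinically significant must be repeated under 6.17.9, and nothing says follow-up samples share the visit label. Finally, no re-test interval is given, so a particular effect around the concentration peak cannot be shown.

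**Conclusion.** The point holds in conditional form. If an out-of-range post-dose vital sign is re-measured and the re-test carries the same nominal timepoint, SAP 5.4 as written replaces the abnormal reading. PCS counts are then biased downward and by-timepoint means are pulled towards the normal range. Nothing in the SAP clearly prevents this.

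The size cannot be fixed from the documents. It depends on re-test labelling, on the correlation between readings and on where each limit sits in the distribution. With exchangeable normal readings and correlation 0.7 to 0.9, the rule gives about 32 to 66% of the first-reading rate where trigger equals limit, and about 66 to 96% for systolic pressure above 150 mmHg. The first range should not be carried over to the nine limits whose trigger is wider.

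The same can happen in the laboratory by-visit tables (thyroid PCS, chemistry and hematology shifts), but only if re-tests share the visit label. The planned laboratory minimum/maximum summaries guard against it only if superseded values are eligible, which the SAP does not state.

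**What to change.** Amend SAP 5.4 before database lock:

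- For post-dose by-timepoint summaries of vital signs and laboratory tests, use the original scheduled reading.
- State that PCS incidence and minimum/maximum post-baseline *will* (not *may*) use all post-baseline readings, including superseded first readings, re-tests and unscheduled values.
- Identify re-tests in the analysis data.
- Keep the later-value rule for the pre-dose baseline, and leave the ECG triplicate mean and the highest-of-three peak flow unchanged.

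The cost is SAP wording and minor programming; trial conduct does not change. The downside is that any-reading PCS counts will be somewhat higher than single-reading rates, because subjects with an out-of-range value are measured more than once. A table footnote should say so.
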